4.0 Study Endpoints

The primary efficacy endpoint is reduction in alcohol use (total standard drinks), compared between NAC and placebo groups. Additional outcomes of interest include agreement between self-report (mobile technology-delivered daily self-report, Timeline Follow-Back) and biomarkers (ethyl glucuronide, carbohydrate deficient transferrin, phosphatidylethanol, alcohol breathalyzer) of alcohol use, as well as agreement between measures of medication adherence (mobile technology-delivered video of medication taking, Medication Event Monitoring System, pill count, self-report).

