Following completion of screening/baseline assessments and determination of study eligibility, participants who return for the randomization visit and continue to be eligible will be randomly assigned to one of the two conditions (NAC or placebo) for 8 weeks of treatment. Random assignment will be on a 1:1 ratio to one of the two conditions. Randomization will be stratified by school status [in secondary school (i.e., middle or high school) versus not] and by sex (female versus male). Adolescents no longer in secondary school (i.e., dropped out, graduated, working, and/or enrolled in college) may have different psychosocial contexts and contingencies related to alcohol use, compared to those still in secondary school. The sex stratification will help avoid significantly discrepant representation of sex across treatment groups, allowing for exploration of potential sex differences in study outcomes. We considered additional stratification variables (e.g., severity of AUD, co-occurring other substance use disorders, history of attention-deficit/hyperactivity disorder), but, amid concern over excessive division of participants among multiple cells, judged that these could be adequately explored as covariates during efficacy analyses.

[name], the study statistician, will generate the randomization schedule using a stratified permuted random block design with block sizes of 2, 4 and 6 to ensure lack of predictability along with relative equality of assignment across treatment groups. All study staff, the investigative team, and participants will remain blind to study assignments until the completion of the study, unless an unblinding is deemed medically necessary. [name] will review randomization data on a regular basis to ensure that the scheme is being implemented according to plan. A randomization slot, once used, will not be re-allocated.

Treatment

Psychosocial Intervention

All participants will receive 8 weekly brief alcohol intervention sessions from NIAAA's brief alcohol intervention,⁵² which includes motivational interviewing and setting individual goals and action plans, consistent with the current standard-of-care treatment.

Pharmacological Intervention

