Clinical Assessments

The instruments to be used were selected because many are standardized, have good psychometric properties, are widely used, and have been used by our research team.

Timeline Follow-Back, inclusive of detailed quantification of alcohol use, measured in standard drinks, will be conducted at baseline to characterize self-reported alcohol and other substance use.⁵³ This approach will be enhanced during trial participation by the implementation of mobile technology-delivered daily alcohol and other substance use reports, using methods established by our research team (see Preliminary Studies).⁴⁰ At baseline assessment and during each daily survey, participants are shown visuals and provided the definition of a standard drink to aid in reporting. The survey expires at midnight so that participants cannot access an old survey. A traditional Timeline Follow-Back will be conducted during laboratory visits to fill in missing data. These alcohol use quantification strategies will be used in calculating primary efficacy outcome measures, including total standard drinks, compared between the 4 weeks prior to intake and the last 4 weeks of study treatment. The trial is powered to test this primary outcome (see *Statistical Methods*), and other alcohol use-related outcomes are exploratory at this Phase II stage of investigation.

The MINI International Neuropsychiatric Interview will be conducted at the initial assessment visit to evaluate for psychiatric and substance use disorders.^{54,55} Throughout the study, a variety of self-report and clinician-administered measures (summarized in the **Study Timetable**) will be collected. In general, these measures will be used to assess and track mental health, substance use-related problems, quality of life, and other functional outcomes over the course of study participation as exploratory aims. Adverse events will

be documented, rated for severity and relatedness, coded in Medical Dictionary for Regulatory Activities (MedDRA) terms, and managed/reported appropriately via established procedures (see Human Subjects section). To evaluate penetration of the blind, participants and the primary study personnel who interact with the participant will be asked at multiple time points whether they think the participant is receiving NAC or placebo.

Laboratory Tests

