12.0 Data Management

Statistical Methods

Power and Sample Size

This Phase II proof-of-concept trial is powered on the primary hypothesis that there will be a clinically significant differential in the decrease in total standard alcohol drinks and drinks per drinking day during the final four weeks of treatment (weeks 5-8) in the NAC group compared to the placebo group. In the proposed study, the two treatment arms, NAC and placebo, will be assessed for differences in drinking behavior using general linear models. In a prior pilot trial assessing adolescent drinking behavior (N=11), our team noted an average total of 49 (SD=26) drinks with 5.5 (2.0) drinks per drinking day during the 4 weeks prior to study enrollment. Additionally, although the participants noted in our prior CUD trial were not required to exhibit AUD nor was treatment targeted at drinking behavior, the heavier drinkers in the study (upper quartile of total drinks prior to baseline, ≥ 24 drinks/30 days) reported a mean of 58 (SD=30; median=54 drinks) drinks during the 4 weeks prior to study entry.²⁶ In this sample of heavier drinkers, those randomized to placebo had a median 10.7% decrease in total drinks at the end of CUD treatment (last 4 weeks of study treatment) as compared to a median 33.0% decrease in total drinks in the NAC treated group. Assuming a more robust treatment effect when alcohol use is the therapeutic target, a 50% decrease in total drinks during the final 4 weeks of study treatment in the active treatment group, as compared to baseline, would be a clinically relevant treatment effect. We conservatively estimate a similarly more robust 20% decrease in total drinks in the placebo treated group. Assuming similar baseline drinking behavior to the adolescent study (baseline mean=49 drinks/4 weeks) and a similar group level variance estimate as in the baseline study data (SD=25), we will have 80% power with a 5% type I error rate to detect the clinically relevant difference between a 50% decrease in the NAC treated group and 20% decrease in the placebo treated group (equivalent to 25 total drinks versus 40 total drinks during the final 4 weeks of treatment) with 45 participants randomized to each treatment group (n=90 total). Additionally, we anticipate that retention may be a challenge in this population, and we anticipate a 25% drop-out rate during study treatment, inflating the necessary randomized sample size to n=60 participants per treatment arm (N=120total randomized participants). The noted sample will have greater than 90% power to find a

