
Version: 16; Version Date: 11JULY2023

corresponding 50% decrease in drinks per drinking day in the NAC treated group as compared to a 20% decrease in the placebo treated group [2.8 (SD=2.0) vs. 4.4 (2.0) drinks per drinking day].

Primary Data Analysis

Baseline clinical and demographic characteristics will be collected and contrasts of baseline characteristics and clinical predictors of substance use will be performed between groups. Continuous and ordinal characteristics will be compared using a Wilcoxon Rank-Sum test statistic while categorical characteristics will be compared using a Pearson Chi-Square test statistic. If a baseline characteristic is significantly associated with the outcomes of interest, the corresponding variables will be used as initial covariates in the model analyses. Secondarily, possible covariates will be tested for confounding effects on the models specified and when present, they will be included in the final adjusted model. Specific Aim 1: The primary measure of interest will be the estimated reduction in self-reported standard alcohol drinks and the associated variance around these estimates during the final four weeks of study treatment (weeks 5-8) in those randomized to NAC as compared to those randomized to placebo. The main effect of NAC versus placebo on the total number of standard drinks will be assessed using generalized linear models and modelbased means with associated standard errors will be reported. Analytic models will be computed both unadjusted and adjusted for significant covariates and confounders found in the preliminary analysis. Specific Aim 2: Self-reported drinking (weekly TLFB and mobile technology-delivered daily diary) as well as biomarkers of recent alcohol use (EtG, CDT, PEth, and alcohol breathalyzer) will be collected at study visits. Agreement between collection measures will be measured as percent agreement and kappa coefficients. Agreement will be assessed weekly during the entire time course of the treatment study and deviations between self-reported moderate/heavy use and biomarker-indicated moderate/heavy use will be assessed to characterize the reporting (under-reporting) of self-reported use amounts. Similarly, medication adherence will be measured at weekly study visits using self-report (self-report and mobile technology delivered video) and MEMS. Concordance percentages and kappa coefficients will be calculated between the adherence measurement methods. Due to high prevalence of self-reported adherence in substance use disorder studies, kappa coefficients will be calculated as the prevalence adjusted bias adjusted kappa (PABAK).⁶² Clustered logistic regression model using the methods of generalized estimating equations will be applied to assess the differences in self-reported drinking and medication adherence measurement methods on binary adherence outcomes over time.⁶³ Working correlation structures will be independently compared and the final model structures will be chosen using the quasilikelihood under the independence model criterion statistic.⁶⁴ The main effects of measurement method and visit, as well as the interaction between method and visit, will examined for significance.

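### Aim 1 is analysed both unadjusted and with data-selected covariates, no rule says which result decides, and neither baseline drinks nor the randomisation strata are fixed terms

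*Combined protocol and SAP*

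**What the plan says.** Section 12.0, Primary Data Analysis, builds the Aim 1 analysis in three steps.

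- Screening: "If a baseline characteristic is significantly associated with the outcomes of interest, the corresponding variables will be used as initial covariates". No candidate list or significance threshold is given.
- Confounding: "possible covariates will be tested for confounding effects on the models specified and when present, they will be included in the final adjusted model". No criterion for confounding is given.
- Reporting: "Analytic models will be computed both unadjusted and adjusted for significant covariates and confounders found in the preliminary analysis".

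The model itself is described only by its family: "The main effect of NAC versus placebo on the total number of standard drinks will be assessed using generalized linear models".

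Section 10.0, Randomization, says "Randomization will be stratified by school status" and also by sex. It leaves other prognostic variables, such as AUD severity, to be explored as covariates. The statistical section never names school status, sex or baseline drinks as model terms. Section 13.0, Quality Assurance, adds that adjustment may follow from a look at baseline comparability. Section 12.0, Secondary Data Analysis, carries a similar model-building process to Weeks 12 and 26.

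The role of baseline drinking is described in two ways. Section 4.0 says "The primary efficacy endpoint is reduction in alcohol use (total standard drinks), compared between NAC and placebo groups", and section 10.0, Clinical Assessments, describes total drinks "compared between the 4 weeks prior to intake and the last 4 weeks of study treatment". Both suggest change from baseline. The model sentence quoted above refers to total drinks, and the power calculation contrasts final totals: "equivalent to 25 total drinks versus 40 total drinks during the final 4 weeks of treatment".

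**The concern.** Two analyses of the same primary comparison are planned and neither is ranked. If they land on opposite sides of 5%, the document offers no way to say whether Aim 1 was met. The content of the adjusted model is also unknown until the outcome data have been examined.

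The unadjusted model has two readings, final totals or change from baseline, and these can differ from each other as well.

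Baseline drinking is likely to be a strong predictor of later drinking, and it is collected on everyone. Leaving it to a screen means that the deciding analysis may or may not use it. Section 1.0 says the trial is to supply effect size estimates for Phase III, and that purpose needs one estimate named in advance.

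**Working it through.** **Inputs from section 12.0, Power and Sample Size.** Final totals of 25 and 40 drinks, so a difference of 15; SD 25; 5% type I error; 45 per arm before dropout; 25% dropout; 60 per arm randomised. Sidedness is not stated. A two-sided test reproduces the plan's number, whereas a one-sided test would need only 35 per arm.

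**Assumed.** The correlation r between baseline and final four-week totals is not in the document, so 0.3, 0.5 and 0.7 are used. The outcome is taken as normal with SD 25 at both times.

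**Step 1: the plan's own figure.** A two-sample t-test with difference 15, SD 25 and 45 per arm has 80.4% power. The dropout inflation is 45/(1 - 0.25) = 60. The stated sample size therefore stands, and it rests on unadjusted final totals.

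**Step 2: power under each possible Aim 1 model.** The effective SDs are:

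- Final total: 25.
- Baseline drinks as a fixed covariate: 25 × √(1 - r²) = 23.8, 21.7, 17.9 (one further degree of freedom lost).
- Unadjusted change: 25 × √(2(1 - r)) = 29.6, 25.0, 19.4.

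| Model | 45 per arm, r = 0.3 / 0.5 / 0.7 | 60 per arm, r = 0.3 / 0.5 / 0.7 |
|---|---|---|
| Final total, unadjusted | 80.4% for all r | 90.3% for all r |
| Change, unadjusted | 66.2 / 80.4 / 95.3% | 78.7 / 90.3 / 98.8% |
| Baseline drinks fixed | 83.9 / 90.1 / 97.6% | 92.7 / 96.4 / 99.5% |

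The 60-per-arm column applies only if every participant is observed. The planned dropout puts the trial nearer the 45-per-arm column.

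**Step 3: how often two analyses split at 5%.** These are simulated at the planned effect. For the data-selected model, 10 candidate covariates were assumed, one of them baseline drinks, with entry at p<0.05 against the outcome.

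| Pair | 45 per arm, r = 0.3 / 0.5 / 0.7 | 60 per arm, r = 0.3 / 0.5 / 0.7 |
|---|---|---|
| Final total, unadjusted vs data-selected (the plan's pair) | 7 / 13 / 18% | 4 / 7 / 9% |
| Final total, unadjusted vs baseline fixed | 7.0 / 12.3 / 17.9% | 4.1 / 7.2 / 9.4% |
| Change, unadjusted vs baseline fixed | 21.4 / 12.4 / 2.9% | 15.8 / 7.1 / 0.9% |
| Final total vs change, both unadjusted | 26.6 / 22.3 / 19.8% | 18.9 / 13.2 / 10.0% |

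The splits in the plan's pair do not all run one way. At r = 0.3 and 45 per arm, the unadjusted result is the significant one in about 2.8 of the 7.0 points.

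**Step 4: what selection itself costs.** At 45 per arm on final totals, the data-selected model has power 81.6/89.5/97.5%, against 83.1/90.3/97.6% with baseline fixed in the same runs. On change it has 82.1/90.0/97.1%, against 82.4/90.7/97.6%. The loss is therefore about 0.1 to 1.5 points. Its rejection rate with no treatment effect is 4.6 to 5.2%.

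**Step 5: why fixing baseline settles final total versus change.** Write the final total as Y, baseline as X and treatment as T, with Y = a + bT + cX + error. Subtracting X from both sides gives Y - X = a + bT + (c - 1)X + error. The treatment coefficient b, its standard error and its p-value are identical. This holds for a normal linear model.

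**Step 6: strata.** Suppose school status and sex explain an assumed 2, 5 or 10% of outcome variance. Adding them to the unadjusted model moves power from 80.4% to about 81, 82 or 84%, a gain of roughly 1 to 4 points. On top of baseline adjustment, taking those shares of the remaining variance, the gain is about 0.2 to 3.6 points depending on r.

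**The case against.** The strongest reply is that the practical loss is small. Baseline drinks would usually pass the screen: in simulation they enter in about 79% of trials at r = 0.3 and in more than 99% at r = 0.5 or above. The planned adjusted model therefore already recovers nearly all of the power gain, and each model taken alone holds its 5% level. This is correct, and it removes any charge that selection damages the analysis. It does not say which result decides.

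A second reply is that the text leans one way or the other. The selection sentence speaks of a final adjusted model, while the power calculation is unadjusted. These hints point in opposite directions, and the Aim 1 sentence then lists both models without ranking them.

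A third reply concerns the model family. The plan writes generalized linear models in one place and general linear models in another, and it expects count distributions for the weekly data. Under a log link the equivalence in Step 5 fails. This stands as a limit on that argument. Naming weeks 5-8 total drinks as the outcome still settles final total versus change under any link.

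Finally, this is a proof-of-concept trial. However, section 10.0 says it is powered to test this primary outcome.

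**Conclusion.** The concern holds, as something that should be fixed. The document plans two Aim 1 results, gives no rule for choosing between them, and fixes neither baseline drinks nor the strata in either model. A split verdict in the plan's own pair is a realistic outcome, at about 7 to 18% of trials with 45 per arm and 4 to 9% if all 60 per arm are observed. The size depends on the assumed correlation, normality and candidate list; the gap in the text does not.

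No stated number is broken and N=120 stands. No false-positive inflation is claimed for the plan as written. A rate of about 6 to 9% was simulated only for the case where the more favourable model is chosen after both results are seen, which a pre-named model prevents.

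**What to change.** Before unblinding, state one primary Aim 1 model in section 12.0:

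- Outcome: total standard drinks in weeks 5-8.
- Terms: treatment, baseline total drinks over the four weeks before intake (as section 10.0 already defines them), school status and sex, all fixed.
- No selection of terms by p-value or by observed imbalance.

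The same sentence should give the distribution, link and effect measure, so that the estimate passed to Phase III is fully defined. Label the unadjusted and data-selected models as sensitivity analyses. Bring the Quality Assurance remark on baseline comparability (section 13.0) and the Week 12 and Week 26 analyses into line.

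The cost is protocol and SAP wording only. Baseline drinks, school status and sex are already collected, and no visits or participants are added.

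### School status and sex define the randomization strata, but no Aim 1 model is fixed to include them, and neither of the two planned models is named as primary

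*Combined protocol and SAP*

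**What the plan says.** Section 10.0 Study Design / Methods, under Randomization, states "Randomization will be stratified by school status" (in secondary school or not) and, in the same sentence, by sex. The schedule is a "stratified permuted random block design with block sizes of 2, 4 and 6", with 1:1 allocation, so the two factors form four strata.

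The same paragraph names further candidates (AUD severity, other substance use disorders, history of ADHD), declines to stratify on them, and "judged that these could be adequately explored as covariates during efficacy analyses". That remark concerns variables left out of the stratification. It does not say how the two factors that were used will be analysed.

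Section 12.0 Data Management, under Primary Data Analysis, gives two routes into a model. The first is association with outcome: "If a baseline characteristic is significantly associated with the outcomes of interest, the corresponding variables will be used as initial covariates in the model analyses". The second is a confounding check: "possible covariates will be tested for confounding effects on the models specified and when present, they will be included in the final adjusted model". For Specific Aim 1 it then says "Analytic models will be computed both unadjusted and adjusted for significant covariates and confounders found in the preliminary analysis". School status and sex are not mentioned there, nor under Secondary Data Analysis or Missing Data and Attrition. No threshold for significance is given, and neither model is designated as primary.

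**The concern.** Stratified blocking balances the arms on school status and sex, so these factors contribute little to chance differences between NAC and placebo. A model that omits them still counts their variance as residual noise. Where the factors predict drinking, its model-based standard error exceeds the real sampling error, the interval is too wide, and the test rejects too rarely under the null. Precision that the design has already secured is not used.

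The adjusted model has a different weakness. Whether a design factor enters depends on a test against the trial's own outcome, so the estimator is not fixed in advance. With no primary model named, the headline NAC effect could come from either. This matters in a trial meant to supply effect size estimates for Phase III.

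**Working it through.** **Inputs from 12.0, Power and Sample Size:** 25 versus 40 drinks (difference 15), SD 25, 5% type I error, 80% power, 45 per arm evaluable, 25% dropout, 60 per arm randomized. **From 10.0:** four strata, blocks of 2, 4 and 6, 1:1 allocation. **Assumed:** R², the share of outcome variance explained by the two factors, which the documents do not give; and a 0.05 screening threshold.

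**Step 1. Reproduce the plan's figure.** n per arm = 2(1.96 + 0.84)² × 25² / 15² ≈ 44. Exact t-test power is 0.795 at 44 per arm and 0.804 at 45, so the plan's 45 is right for a two-sided test. 45 / (1 − 0.25) = 60 per arm, 120 in total.

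**Step 2. Large-sample formulas, full balance at 45 per arm.** The unadjusted standard error is 25 × √(2/45) = 5.27, and the standardized effect is 15 / 5.27 = 2.846. Under stratified balance the true standard error is 5.27 × √(1 − R²). Hence:

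- size, unadjusted = 2[1 − Φ(1.96 / √(1 − R²))]
- power, unadjusted = Φ((2.846 − 1.96) / √(1 − R²))
- power, strata fitted = Φ(2.846 / √(1 − R²) − 1.96)

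| R² | SE overstated by | Size, unadjusted | Power, unadjusted | Power, strata fitted |
|---|---|---|---|---|
| 0 | 0% | 5.0% | 81.2% | 81.2% |
| 5% | 2.6% | 4.4% | 81.8% | 83.1% |
| 10% | 5.4% | 3.9% | 82.5% | 85.1% |
| 15% | 8.5% | 3.4% | 83.2% | 87.0% |

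**Step 3. Allow for dropout.** Random loss of 25% partly undoes the balance within strata, so Step 2 overstates the problem. Simulation used 120 randomized, strata of about equal size, equal contributions from the two factors, a normal outcome and 12,000 null runs per setting:

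| R² | Model SE / actual SE, unadjusted | Size, unadjusted | Size, significance-selected | How often the screen selects a factor |
|---|---|---|---|---|
| 0 | 0.99 | 5.2% | 5.2% | 5% |
| 5% | 1.02 | 4.8% | 5.1% | 32% |
| 10% | 1.03 | 4.3% | 5.2% | 57% |
| 20% | 1.08 | 3.3% | 4.7% | 88% |
| 30% | 1.12 | 2.7% | 4.9% | 97% |

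A separate set of runs at R² of 5%, 10% and 15% gave unadjusted sizes of about 4.9%, 4.2% and 3.6%. The differences of 0.1 point are within simulation error: √(0.05 × 0.95 / 12,000) is 0.2 point. With both factors always fitted, size was 4.7% to 5.2% for R² from 0 to 30%.

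**Step 4. Power with dropout, at R² of 5%, 10% and 15%.** Unadjusted: about 81% to 82%. Strata always fitted: 81.6%, 84.2% and 85.5%. Significance-selected: 81.4%, 83.2% and 84.9%. Selection therefore costs 0.2, 1.0 and 0.6 points.

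**The case against.** The strongest reply is that the plan already provides an adjusted model, and that model performs well. The screen usually picks up a factor when omitting it would matter, and tends to miss it only when little is lost. Size stays near 5% and at most about 1 point of power goes. This stands, and it confines the standard-error problem to the unadjusted model. It does not answer the pre-specification point: at an R² of 10% the screen selects a given factor only 57% of the time, so the covariate set depends on the outcome data.

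A reader might go further and infer that the trial's 5% test runs below 5%. The documents do not support that. The 5% appears in the sample-size paragraph, and nothing says which model carries the test.

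Nor do they establish that the strata predict drinking. Section 10.0 says only that adolescents out of secondary school may differ in psychosocial context and contingencies related to alcohol. Sex is stratified for balance and to allow exploration of sex differences; no difference in drinking level is asserted.

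The direction of the error also assumes a correctly specified variance. The power paragraph says general linear models, the analysis paragraph says generalized, and no distribution is named for total drinks. A wrong variance model could make standard errors too small for that separate reason.

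**Conclusion.** The gap is real and modest. Neither stratification factor is guaranteed a place in any efficacy model, and no primary model is named. For R² of 5% to 15%, the unadjusted analysis would run at roughly 4.9% to 3.6% and give up about 1 to 4 points of available power. At R² of zero there is no loss.

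These figures rest on an assumed R², a correctly specified linear model, random dropout, strata of similar size and equal contributions from the two factors. They were not computed for the logistic and count models under Secondary Data Analysis and should not be quoted there. In a logistic model, omitting a prognostic factor also changes the odds ratio being estimated.

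The error is conservative. Unadjusted power still meets the planned 80% under the plan's own inputs, so the sample size of 120 stands. The case for change is that fitting both factors held its size in every setting tested and needs no extra participants.

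**What to change.** In 12.0, Specific Aim 1, name one primary model for total standard drinks that includes treatment, school status and sex, with the latter two as fixed terms whatever their p-values. State that the NAC effect and its confidence interval are read from that model. Keep the unadjusted model and any further-adjusted model as sensitivity analyses.

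For consistency with the design, carry the same two terms into the secondary comparisons between arms, without attaching the linear-model magnitudes to them.

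The cost is one sentence and two degrees of freedom. Both variables are already recorded because randomization requires them.
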